1 PROTOCOL SYNOPSIS

Protocol Title	Prospective, Multi-center, Single-Arm Post-market Study of use of the OMNI® Surgical System in Combination with Cataract Extraction in Open Angle Glaucoma
Protocol ID Number	06213
Study Device	OMNI™ Surgical System
Study Objective	To prospectively assess the clinical effect of ab-interno transluminal viscoelastic delivery and trabeculotomy performed using the OMNI Surgical System in combination with Cataract Extraction on intraocular pressure (IOP) and the use of IOP-lowering medications in patients with mild-moderate open angle glaucoma (OAG).
Study Design	Prospective, multicenter, single-arm, post-market study.
Primary Effectiveness Endpoints	
Reduction in mean unmedicated diurnal IOP from baseline to 12 months; andReduction in mean number of IOP-lowering medications from screening to 12 months
Secondary Effectiveness Endpoint	
Percent of eyes with a ≥20% reduction in unmedicated diurnal IOP at 12 monthsPercent of eyes with unmedicated diurnal IOP between 6 and 18 mmHg inclusive at 12 months
Safety Endpoints	
Rates of ocular adverse events (intraoperative, postoperative)Reduction in best corrected visual acuity (BCVA) from baseline (note: reduction in BCVA due to PCO will not be treated as a safety event)

Inclusion Criteria	Inclusion Criteria
	
Inclusion Criteria (only one eye of each subject is eligible, and all ocular criteria apply to the study eye):
 
 1. Male or female subjects, 22 years or older 2. Visually significant cataract 3. Diagnosed with mild to moderate open angle glaucoma (e.g. primary open angle glaucoma, pigmentary glaucoma, pseudoexfoliative glaucoma) as documented in subjects' medical record per ICD-10 guidelines 4. At screening, a medicated IOP \leq33 mmHg and on 1-4 IOP-lowering medications¹ with a stable medication regimen for two months prior to screening visit 5. At baseline, unmedicated diurnal IOP 21-36 mmHg and IOP at least 3 mmHg higher than screening IOP 6. Scheduled for cataract extraction followed by ab-interno transluminal viscoelastic delivery and trabeculotomy using the OMNI Surgical System 7. Shaffer grade of \geq III in all four quadrants 8. Potential of good best corrected visual acuity post cataract extraction, in the investigator's judgment 9. Able and willing to comply with the protocol, including all follow-up visits. 10. Understands and signs the informed consent

¹ For combination IOP-lowering medications that consist of two or more IOP-lowering drugs, each IOP-lowering drug component counts as a separate medication.

Exclusion Criteria	
(All criteria apply to the study eye; both eyes of a single subject need not be eligible):
 
 1. Any of the following prior treatments for glaucoma: 
 o Laser trabeculoplasty \leq 3 months prior to baseline o Implanted with iStent, Cypass, Xen, Express, glaucoma draining device/valve, or Hydrus Device o Prior canaloplasty, goniotomy, trabeculotomy, trabeculectomy, ECP or CPC 2. Normal tension glaucoma 3. Acute angle closure, traumatic, congenital, malignant, uveitic or neovascular glaucoma 4. Severe glaucoma as documented in subjects' medical record per ICD-10 guidelines 5. Use of oral hypotensive medication treatment for glaucoma 6. In the investigator's judgement, predisposed to significant risk because of washout of ocular hypotensive medications 7. Ocular pathology or medical condition which, in the investigator's judgment, would either place the subject at increased risk of complications, contraindicate surgery, place the subject at risk of significant vision loss during the study period (e.g., wet AMD, corneal edema, Fuch's dystrophy, etc.), or interfere with compliance to elements of the study protocol (e.g., returning to investigator's office for follow-up visits) 8. Participation (\leq 30 days prior to baseline) in an interventional trial which could have a potential effect on the study outcome, as determined by the study investigator 9. Women of childbearing potential if they are currently pregnant or intend to become pregnant during the study period; are breast-feeding; or are not in agreement to use adequate birth control methods to prevent pregnancy throughout the study
Number of Subjects Enrolled and Treated	A total of 145 subjects will be enrolled and treated.
Number of Sites	Up to 20

Study Duration for Each Subject	12 months
Total Study Duration	Approximately 24 months
Schedule of Visits	Screening, Baseline, Surgery (Day 0), Day 1, Week 1, 1 Month, 3 Month, 6 Month, 12 Month, 12 Month Washout (if applicable)
Treatments	Cataract extraction followed by ab-interno transluminal viscoelastic delivery and trabeculotomy using the OMNI Surgical System

2 STUDY OBJECTIVE

The objective of this study is to prospectively assess the impact of ab-interno transluminal viscoelastic delivery and trabeculotomy performed using the OMNI Surgical System in combination with cataract extraction on intraocular pressure (IOP) and the use of IOP-lowering medications in patients with mild to moderate open angle glaucoma (OAG).

Trabeculectomy and tube-shunt implantations remain the gold standard for surgical management of IOP.⁷ These interventions are associated with a long list of potential complications such as sclero-conjunctival scarring, hypotony, hypotony maculopathy, choroidal detachment, conjunctival leak, hyphema, and bleb related complications.⁸ Surgical techniques that re-establish the aqueous outflow through the physiological pathways without the need for a bleb are gaining acceptance among glaucoma surgeons.⁹ Canaloplasty is one such procedure that is intended to restore the natural aqueous outflow system through microcatheterization and viscodilation of the entire length of the Schlemm's canal with a well-documented safety and efficacy profile in reducing IOP.^{10,11} Trabeculotomy is another such procedure that relieves the resistance to aqueous flow by cleaving the trabecular meshwork and the inner walls of Schlemm's canal.¹²

The OMNI™ Surgical System (Sight Sciences Inc, Menlo Park, CA) is a 510K-cleared manually operated device indicated for the delivery of small amounts of viscoelastic fluid and to cut trabecular meshwork tissue during trabeculotomy procedures. The

⁶ Newman-Casey PA, Robin AL, Blachley T, Farris K, Heisler M, Resnicow K, Lee PP. The Most Common Barriers to Glaucoma Medication Adherence: A Cross-Sectional Survey. *Ophthalmology*. 2015 Jul; 122(7):1308-16.

⁷ Gedde SJ, Singh K, Schiffman JC, Feuer WJ. The Tube Versus Trabeculectomy Study: interpretation of results and application to clinical practice. *Curr Opin Ophthalmol*. 2012 Mar; 23(2):118-26.

⁸ Zahid S, Musch DC, Niziol LM, Lichter PR, Collaborative Initial Glaucoma Treatment Study Group. Risk of endophthalmitis and other long-term complications of trabeculectomy in the Collaborative Initial Glaucoma Treatment Study (CIGTS). *Am J Ophthalmol*. 2013 Apr; 155(4):674-680, 680.e1.

⁹ American Academy of Ophthalmology. Preferred practice pattern®. Primary open-angle glaucoma. San Francisco, CA. 2015.

¹⁰ Klink T, Sauer J, Körber NJ, et al. Quality of life following glaucoma surgery: canaloplasty versus trabeculectomy. *Clin Ophthalmol*. 2014;18:9:7-16.

¹¹ Lewis RA, von Wolff K, Tetz M, Körber NJ, Kearney JR, Shingleton B, Samuelson TW. Canaloplasty: circumferential viscodilation and tensioning of Schlemm's canal using a flexible microcatheter for the treatment of open-angle glaucoma in adults: interim clinical study analysis. *J Cataract Refract Surg* 2007; 33:1217-1226

4 STUDY DEVICE

4.1 INDICATIONS FOR USE

The OMNI Surgical System has been 510k cleared by the US Food and Drug Administration (FDA) for the following indication for use²⁵:

The OMNI® Surgical System is indicated for canaloplasty (microcatheterization and transluminal viscodilation of Schlemm's canal) followed by trabeculotomy (cutting of trabecular meshwork) to reduce intraocular pressure in adult patients with primary open-angle glaucoma. . .

4.2 DEVICE DESCRIPTION

The OMNI™ Surgical System ("OMNI") is a sterile, single use, manually operated instrument used by ophthalmologists to deliver small, controlled amounts of viscoelastic into the anterior segment of the eye during ophthalmic surgery. It is also indicated to cut trabecular meshwork tissue during trabeculotomy procedures.

The OMNI is designed to function with commonly used viscoelastic fluids made commercially available by companies such as Abbott Medical Optics (AMO), Bausch & Lomb, and Alcon. The OMNI dispenses fluid on the principle of exchanging volumes much like a syringe. The handheld instrument includes a cannula, microcatheter, internal reservoir and plunger tube, and finger wheels. The finger wheels on the handle of the device are used to advance and retract the microcatheter. In addition, when the device is being used to deliver viscoelastic, retraction of the microcatheter causes the

²³ Zhang ML, Hirunyachote P, and Jampel H. Combined surgery versus cataract surgery alone for eyes with cataract and glaucoma. Cochrane Database Syst Rev. 2015; 7: CD008671

²⁴ Vold S, Ahmed II, Craven ER, Mattox C, Stamper R, Packer M, Brown RH, Ianchulev T; CyPass Study Group. Two-Year COMPASS Trial Results: Supraciliary Microstenting with Phacoemulsification in Patients with Open-Angle Glaucoma and Cataracts. Ophthalmology. 2016 Oct;123(10):2103-12. doi: 10.1016/j.ophtha.2016.06.032.

²⁵ OMNI 510k K202678 approval

[figure not shown]
<https://www.accessdata.fda.gov/scripts/cdrh/cfdocs/cfpmn/pmn.cfm?ID=K202678>

plunger tube to advance into the viscoelastic fluid reservoir thereby dispensing viscoelastic fluid.

The microcatheter can be advanced/retracted up to 20 mm per cycle. The microcatheter can be fully advanced/retracted up to 5 times (i.e. 5 full cycles of 20 mm each). Dispensation of viscoelastic can only occur during the first two 20-mm cycles.

The wheels are located on both sides of the handle. This allows the OMNI device to be used in either eye (OD or OS) and in either hand of the surgeon (left or right), by turning the device 180 degrees along its vertical axis.

Figure 1: OMNI Surgical System

4.3 TRAINING

[figure not shown]
Investigators participating in the study must be experienced in using the OMNI Surgical System (i.e. they must have performed at least 5 procedures with the OMNI Surgical System). All study staff will receive training on the protocol and execution of the study according to applicable regulations and Good Clinical Practices.

5 PRIORITY INVESTIGATIONS

Several case series studies have been performed to evaluate the results of ab-interno transluminal viscoelastic delivery and trabeculotomy performed with the OMNI device in patients with open angle glaucoma.

Grabska-Liberek, et al reported on 10 eyes (9 patients) with open angle glaucoma.²⁶ Five eyes were treated with OMNI surgery alone and 5 eyes underwent OMNI surgery plus cataract extraction (OMNI + CE). In the 5 OMNI alone eyes, IOP declined from an average of 20.4 mmHg pre-op to 12.6 mmHg at 6 months (38.2% decline) and in the OMNI + CE, IOP declined from 16.4 mmHg pre-op to 11.2 mmHg at 6 months (31.7% decline). Use of IOP-lowering medications also declined in both groups: from an average of 3.6 pre-op to 0.4 at 6 months (OMNI surgical) and 2.8 to 0.4 in the OMNI+CE group. Early post-operative complications included IOP spikes (5 cases), hyphema (6 cases), and fibrin in the anterior chamber (1 case). IOP spikes were observed 1-2 days after surgery and were treated with systemic drugs (e.g. acetazolamide or mannitol). Hyphema resolved within the first week post-op.

Figure 2: Results for OMNI Surgery (Grabska-Liberek et al)

Martinez-Rubio, et al²⁷ reported early safety and efficacy of viscodilation and trabeculotomy using the OMNI Surgical System in 20 eyes with primary open angle glaucoma, 13 of which were treated with the OMNI device and cataract surgery and 7 who were only treated with the OMNI device. Mean pre-operative IOP was 24.2 ± 6.3 mmHg and the mean number of preoperative antiglaucoma drugs used by patients was 2.7. At 6 months, pressure had been reduced to an average of 15.9 ± 3.3 and medications were reduced to an average of 1.1. Early postoperative complications included one case of transient toxic anterior segment syndrome (TASS) and one case of transient hyphema. Early follow-up data showed a reduction of IOP, with medication reduction, in treatment of moderate glaucoma in adults.

²⁶ Grabska-Liberek I, et al. OMNI 360 in Open-Angle Glaucoma Treatment: A 6-Month Follow-Up. European Society of Cataract & Refractive Surgeons (ESCRS) 2018.

²⁷ Martinez-Rubio, et al. OMNI-an initial experience with a new surgical glaucoma treatment device. European Society of Cataract & Refractive Surgeons (ESCRS) 2018.

Figure 3: Results for OMNI Surgery (Martinez-Rubio et al)

6 STUDY DESIGN

This is a prospective, multicenter, single-arm, post-market study.

6.1 STUDY DEVICE

The study device is the OMNI Surgical System. Subjects enrolled in the study will undergo ab-interno transluminal viscoelastic delivery and trabeculotomy using the OMNI Surgical System in conjunction with cataract extraction.

6.2 STUDY SITES

This study will be conducted at up to 20 sites in the United States. No center will have more than 25% of the target enrollment.

7 STUDY ENDPOINTS

7.1 EFFECTIVENESS ENDPOINTS

The **Primary effectiveness endpoints** are:

- Reduction in mean unmedicated diurnal IOP from baseline to 12 months; and
- Reduction in mean number of IOP-lowering medications from screening to 12 months

The **Secondary effectiveness endpoints** are:

- Percent of eyes with a $\geq 20\%$ reduction in unmedicated diurnal IOP at 12 months
- Percent of eyes with unmedicated diurnal IOP between 6 and 18 mmHg inclusive at 12 months

7.2 SAFETY ENDPOINTS

Safety will be assessed by evaluating the following measures over time:

- Rates of ocular adverse events (intraoperative, postoperative)
- Reduction in best corrected visual acuity (BCVA) from baseline (note: reduction in BCVA due to PCO will not be treated as a safety event)

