8 STUDY SELECTION CRITERIA

8.1 INCLUSION CRITERIA

For inclusion in this study, subjects must meet all the following criteria (only one eye of each subject is eligible, and all ocular criteria apply to the study eye only unless otherwise indicated):

1. Male or female subjects, 22 years or older
2. Visually significant cataract
3. Diagnosed with mild to moderate open angle glaucoma (e.g. primary open angle glaucoma, pigmentary glaucoma, pseudoexfoliative glaucoma) as documented in subjects' medical record per ICD-10 guidelines
4. At screening, a medicated IOP \leq 33 mmHg and on 1-4 IOP-lowering medications with a stable medication regimen for two months prior to screening visit²⁸
5. At baseline, unmedicated diurnal IOP 21-36 mmHg and IOP at least 3 mmHg higher than screening IOP
6. Scheduled for cataract extraction followed by ab-interno transluminal viscoelastic delivery and trabeculotomy using the OMNI Surgical System
7. Shaffer grade of \geq III in all four quadrants
8. Potential of good best corrected visual acuity post cataract extraction, in the investigator's judgment
9. Able and willing to comply with the protocol, including all follow-up visits
10. Understands and signs the informed consent.

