9 STUDY PROCEDURES

9.1 STUDY SCHEDULE

Table 1: Study Visit Schedule

Note: The fellow eye should be followed per the PI's usual practice based on the ocular health of the fellow eye.

PROCEDURE	SCREENING (DAY -45 TO -6)	BASELINE (DAY -7 TO 0)	SURGERY (DAY 0)	1 DAY (DAY 1)	1 Wk (DAY 5-9)	1 M (DAY 21-35)	3 M (DAY 70-98)	6 M (DAY 150-210)	12 M (DAY 330-420)	12 M WASHOUT ²⁹ (DAY 330-420)
Informed Consent	X									
Demographics	X									
Medical & Ocular History	X	X								
Medication Log	X	X	X	X	X	X	X	X	X	X
BCVA (ETDRS), with manifest refraction	X	X			X	X	X	X	X	
Visual Field (Humphrey 24-2 SITA)	X									X
IOP (Goldmann)	X			X	X	X	X	X	X ³⁰	
Unmedicated diurnal IOP (Goldmann)		X							X ³¹	X
Slit Lamp Exam	X	X		X	X	X	X	X	X	
Gonioscopy	X				X	X	X	X	X	
Dilated Fundus Exam/C:D Ratio	X								X	
Eligibility Assessment	X	X								
Cataract Extraction + ab-interno transluminal viscoelastic delivery and trabeculotomy			X							
AE Assessment	X	X	X	X	X	X	X	X	X	X

²⁹ The 12 month washout visit is only required for subjects who are taking hypotensive medications at the 12 month visit.

³⁰ This is only required for subjects who are taking hypotensive medications at the 12 month visit.

³¹ If subject is not on any hypotensive medications, a diurnal IOP measurement should be obtained at the 12 month visit as unmedicated IOP.

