10.2 LIST OF ANTICIPATED POTENTIAL ADVERSE EVENTS

Anticipated potential adverse events listed below include those that might reasonably be expected to occur in this study because they are associated with glaucoma, cataract surgery, ab-interno transluminal viscoelastic delivery, trabeculotomy, and/or the risk analysis for OMNI System. Adverse events may occur intra-operatively or post-operatively.

- Layered Hyphema $\geq 1\text{mm}$ (Microhyphema or Hyphema $<1\text{mm}$ is expected and will not be considered an AE)
- IOP increase $\geq 10\text{ mmHg}$ above baseline IOP at ≥ 1 month visit³³
- IOP increase requiring management with systemic medication at ≥ 1 month visit³²
- Need for secondary surgical intervention to manage IOP³²
- Hypotony (IOP $<6\text{ mmHg}$)³⁴ with at least one of the following conditions:
 - Flat anterior chamber requiring anterior chamber reformation
 - Corneal folds
 - Choroidal effusions requiring or undergoing surgical drainage
 - Suprachoroidal hemorrhage

³³ To avoid double counting an event, events of IOP $\geq 10\text{ mmHg}$ above baseline IOP at ≥ 1 month visit that require management with systemic medication or secondary surgical intervention should be reported as “IOP increase requiring management with systemic medication at ≥ 1 month visit” or “Need for secondary surgery intervention to manage IOP,” respectively.

³⁴ Hypotony is defined as “early” if it occurs within 2 weeks of surgery and “late” if it occurs more than 2 weeks after surgery

e) Maculopathy

- Corneal injury
- Corneal edema after 1 week
- Corneal abrasion
- BCVA loss of ≥ 10 letters (ETDRS) at or after 3 months postoperative
- Descemet's membrane tear or detachment
- Chronic anterior uveitis (inflammation of grade 1+ or worse persisting for more than 3 months post-operatively or that recurs less than three months after discontinuing treatment)
- Wound leak
- IOL dislocation and/or damage
- Intracorneal Hematoma
- Posterior capsular tear
- Pupillary block
- Cyclodialysis
- Iridodialysis or significant iris damage
- Peripheral Anterior Synechiae > 1 clock hour
- Suture abscess or other local infection
- Flat or shallow anterior chamber requiring anterior chamber reformation
- Aqueous misdirection
- Choroidal detachment
- Choroidal effusion requiring surgical drainage
- Choroidal hemorrhage
- Suprachoroidal hemorrhage
- Vitreous hemorrhage
- Perforation of sclera
- Clinically significant cystoid macular edema
- Retinal detachment
- Retinal tear

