11.5.2 BEST CORRECTED VISUAL ACUITY (BCVA)

The number and percent of eyes reporting with BCVA of 20/20 or better, 20/25 or better, 20/32 or better, 20/40 or better, worse than 20/40 to 20/80, worse than 20/80 to 20/200, and worse than 20/200 at each visit will be summarized. The number and

percent of eyes reporting BCVA of increase \geq 10 letters, increase 10 letters, increase \geq 5 letters to < 10 letters, within 5 letters change, decrease \geq 5 letters to < 10 letters, decrease 10 letters, and decrease \geq 10 letters at each postoperative visit will be calculated.

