20.4 VISUAL ACUITY

ETDRS Testing Method

Best-corrected visual acuity at Baseline and all scheduled follow-up visits will be measured using the ETDRS charts at 1 or 4 meters.

The ETDRS chart must be placed at a distance of 4.00 meters (13 feet and 1.5 inches, or 157.5 inches) from cornea to chart surface, when using a 4-meter chart. For the patients unable to read the topmost line of 4.00 meter chart VA testing should be done using 1 meter chart. For testing at 1 meter, the distance must be 1.00 (39 and 3/8 inches). A measuring tape or meter stick should always be available to verify the chart distance, even if the examining chair is supposed to be immovable or if reference marks are placed on the floor or walls. (Custodial and other staff have been known to move room furnishings about and clean-off marks from the floor or wall while performing their duties, necessitating re-establishing the correct distances for the lane.)

The 1-meter distance is measured from the eye of the participant, seated comfortably in a chair with his/her back firmly placed against the chair, to the center of the 2nd or 4th letter of the 3rd line of the chart. The measuring device can be homemade (e.g., a dowel rod accurately cut to a length of 1.00 m) or 1 meter ruler may be purchased.

Note: If it is necessary to refract at the 1-meter distance, remember to add +0.75 sphere to the trial frame. Subtract the +0.75 sphere from the final refraction obtained at the 1-meter distance before recording the refraction on the form.

Methods

The subject should attempt to read each letter, line-by-line, left to right, beginning with line 1 at the top of the chart. The subjects should be told that the chart has letters only, no numbers. If the subject reads a number, he or she should be reminded that the chart contains no numbers, and the examiner should then request a letter in lieu of the number. The subject should be asked to read slowly, about one letter per second, so as to achieve the best identification of each letter. He/she is not to proceed to the next letter until he/she has given a definite response.

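### The BCVA safety endpoint is referenced to acuity before cataract removal, and no within-eye loss from a postoperative value is planned, so the cataract gain can offset later loss.

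*Combined protocol and SAP*

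**What the plan says.** Section 7.2 has two safety measures: rates of ocular adverse events, and "Reduction in best corrected visual acuity (BCVA) from baseline", with loss due to posterior capsule opacification (PCO) set aside. The synopsis and the interim analysis list in 11.6 define the acuity measure in the same way.

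Table 1 in 9.1 places the reference visit before surgery (column "BASELINE (DAY -7 TO 0"). Section 8.1 requires "Visually significant cataract" and also "Potential of good best corrected visual acuity post cataract extraction, in the investigator's judgment".

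Two other places deal with acuity loss:

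- Section 10.2 lists as an anticipated adverse event "BCVA loss of ≥ 10 letters (ETDRS) at or after 3 months postoperative". It does not say from which visit the loss is counted.
- Section 11.5.2 has two summaries. One gives absolute levels at each visit: "The number and percent of eyes reporting with BCVA of 20/20 or better, 20/25 or better, 20/32 or better, 20/40 or better", and so on down to worse than 20/200. The other gives categories of letters gained or lost, where the eyes with each change in "letters at each postoperative visit will be calculated". It names no reference visit.

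Section 20.4 states: "Best-corrected visual acuity at Baseline and all scheduled follow-up visits will be measured using the ETDRS charts". Table 1 schedules postoperative BCVA at Week 1 and at 1, 3, 6 and 12 months. All safety analyses use the ITT population (11.5).

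**The concern.** Change from baseline in this trial is the sum of two effects: the gain from removing the cataract and any later loss. The entry criteria make the gain likely in nearly every eye. An eye that gains 20 letters and then loses 20 has a change from baseline of zero. The study is single-arm, so no cataract-only group is available to separate the two effects.

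The protocol shows that it cares about late loss: its acuity adverse event starts at 3 months, and the endpoint makes an exception for PCO, which develops after the lens is removed. A pre-surgery reference is poorly suited to finding that kind of decline. A reader who saw few eyes below baseline at 12 months could take it as evidence that acuity was maintained after surgery, which the measure does not show.

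**Working it through.** **The plan's own safety figure.** BCVA has no hypothesis, threshold or power of its own. The only safety calculation is in 11.1.3: with 130 eyes, a 95% chance of seeing at least one event whose rate is about 2.4%.

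- 1 − (1 − 0.024)^130 = 95.7%.
- The rate that gives exactly 95% is 1 − 0.05^(1/130) = 2.28%.

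The statement reproduces. It presumes that every event that occurs is counted.

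**Share of later losses visible against baseline.** Let G be the letter gain from cataract removal and L a true later loss. Change from baseline is G − L. It counts as a loss of at least 10 letters only if G − L ≤ −10, that is, G ≤ L − 10. For a normal gain with mean m and standard deviation s,

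P(flagged) = Φ((L − 10 − m)/s).

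The documents give no baseline acuity, no acuity entry limit and no expected gain, so m = 5 to 20 and s = 8 to 12 are assumptions. For L = 15, P(flagged) = Φ((5 − m)/s):

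| Mean gain | SD 8 | SD 12 |
|---|---|---|
| 5 | Φ(0) = 50% | Φ(0) = 50% |
| 10 | Φ(−0.625) = 27% | Φ(−0.417) = 34% |
| 15 | Φ(−1.25) = 11% | Φ(−0.833) = 20% |
| 20 | Φ(−1.875) = 3% | Φ(−1.25) = 11% |

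The range is 3% to 50%. For other losses at SD 8 and mean gains of 5, 10, 15 and 20 letters:

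- L = 10: 27%, 11%, 3% and 0.6%.
- L = 20: 73%, 50%, 27% and 11%.

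Against a postoperative reference, every true loss of at least 10 letters from that reference would be flagged, ignoring measurement error.

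**Effect on the plan's figure.** Suppose 2.4% of eyes truly lose 15 letters after their gain, and a share q of these show against baseline. The chance of seeing at least one is 1 − (1 − 0.024q)^130, and the true rate needed for a 95% chance is 2.28%/q.

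| q | Chance of at least one | True rate needed |
|---|---|---|
| 100% | 95.7% | 2.3% |
| 50% | 79% | 4.6% |
| 10.6% | 28% | 21.5% |

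The last two rows match a mean gain of 5, and a mean gain of 15 with SD 8.

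**What the other summaries would show.** The absolute categories need no baseline, so a fall in acuity across the group would appear in them. They are percentages of eyes at each visit, however, so one eye's decline can be offset by another's improvement. An eye that goes from 20/20 to 20/32 still counts as 20/40 or better.

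**The case against.** The strongest reply is that acuity safety does not rest on the baseline comparison alone. A reader might infer three stronger statements, and the documents do not support them.

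- *That acuity is judged only against baseline.* Section 11.5.2 also tabulates absolute acuity at every visit, and 11.4 allows individual data listings, though as an option.
- *That the adverse event and the letter-change table are tied to the pre-surgery value.* Neither names a reference. Elsewhere in 10.2 the IOP-rise and cup-to-disc events do name baseline, so the omission for BCVA leaves the reference open. Baseline is the natural reading, because it is the only BCVA reference stated for a safety endpoint, but it remains a reading.
- *That an eye which gains and then loses the same number of letters triggers no event.* Section 10 requires ocular adverse events to be documented whether or not they are device related, and 10.1 makes sight-threatening events serious. Section 10.2 lists many causes of late loss with no letter threshold, such as cystoid macular edema, retinal detachment, late corneal edema and endophthalmitis.

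It can also be said that net change from before surgery is a coherent measure for a treatment defined as cataract extraction plus the device, and that the percentages rest on assumed gains. Both points are fair. The first is a reason to keep the baseline comparison. The second is why the figures are given only as an illustration.

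What remains is that none of these routes identifies, eye by eye, a fall from the acuity reached after surgery.

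**Conclusion.** The point holds in limited form. The named BCVA endpoint uses a reference taken before the cataract is removed, two related definitions leave their reference open, and no within-eye loss from a postoperative value is planned. Followed as written, the endpoint sets later loss against the cataract gain.

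The size is uncertain. With a normally distributed gain, mean 5 to 20 letters and SD 8 to 12, about 3% to 50% of true 15-letter later losses would register as a loss of at least 10 letters from baseline. Larger losses or smaller gains would show more often. These are shares under the baseline comparison only; they are not shares of losses missed by the safety assessment as a whole, because the absolute categories and cause-specific adverse events would pick up some of the rest.

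The endpoint is descriptive, so no test, power statement or sample size depends on it. This is a low-cost improvement and does not put the trial's conclusions on effectiveness at risk.

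**What to change.** - **11.5.2:** keep the baseline comparison and state baseline as the reference for the letter-change table.
- **7.2 and 11.5.2:** add a descriptive ITT table of eyes with a loss of at least 10 letters from the 1-month BCVA, at 3, 6 and 12 months. Show it with and without eyes whose loss is attributed to PCO.
- **10.2:** leave the adverse event as it is, apart from naming its reference visit so that up to 20 sites apply the same one.

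The cost is one extra table and some wording. BCVA is already collected at all the visits needed. The protocol edits go through the modification process in section 14, with IRB review as necessary. A few more losses will be reported, some from test-retest noise. A fixed 1-month reference limits this compared with the best prior value, but it may miss loss in eyes still recovering at 1 month.
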